1.0 Background

Pancreatoduodenectomy, commonly referred to as a Whipple procedure, is a complex procedure performed for patients with both benign and malignant diseases of the periampullary region which consists of the head of the pancreas, the second portion of the duodenum near the ampulla of Vater, and the distal common bile duct. Although mortality from the procedure is reported to be less than 5% in high volume centers, morbidity rates are much higher with reports indicating rates around 40% [1, 2]. Two of the most common complications contributing to this high morbidity rate include infections and pancreatic fistulae. Studies have demonstrated that such complications have been associated with increased mortality rates in patients undergoing pancreatic surgery [3].

Many patients undergoing pancreatoduodenectomy already have a biliary stent in place draining their biliary system to prevent obstructive jaundice. While these stents allow for decompression of an obstructed or soon-to-be biliary tree, they are also quick to colonize with enteric flora of the gastrointestinal tract. Patients with preoperative stents have been shown to have higher wound infection and bacteremia rates [4]. Because pancreatoduodenectomy involves resection of the bile duct and construction of a biliary-enteric anastomosis, it is quite likely that contaminated bile is present in the surgical field. These bacteria sitting within the peritoneum are not appropriately treated by intravenous antibiotics and may contribute to local complications such as organ space infections, wound infections, and pancreatic fistulae.

2.0 Rationale and Specific Aims

Antibiotic irrigation during abdominal surgery via peritoneal lavage is used commonly in abdominal surgery when there are concerns about contamination. This technique offers the ability to decrease bacterial load, thereby potentially reducing intra-abdominal infections. While irrigation typically consists of normal saline, several antibiotics have been used with varying degrees of success. Recent literature in the field of colorectal surgery has demonstrated that the intraoperative use of antibiotic irrigation decreases wound complication rates to less than 5% compared to a rate of 14% among those receiving normal saline irrigation [5].

Hypothesis: The routine use of intraoperative antibiotic irrigation during pancreatoduodenectomy will decrease superficial and organ space infections.

Primary Specific Aim:

- Test the efficacy of routine antibiotic irrigation in reducing superficial and organ space infections among patients undergoing pancreatoduodenectomy.

Secondary Specific Aim:

- Test the efficacy of antibiotic irrigation in reducing pancreatic fistula rates.

3.0 Inclusion/Exclusion Criteria

Inclusion Criteria:

- 1) At least 18 years of age and older.
- 2) Open pancreateoduodenectomy for any diagnosis.

Exclusion Criteria:

- 1) Pregnant
- 2) Prisoners
- 3) Patients undergoing concomitant colectomy
- 4) Antibiotic allergy to study medication
- 5) Serum creatinine > 2.0
- 6) Unable to provide informed consent

4.0 Enrollment/Randomization

All patients will be registered with the Surgery Research Office. Regulatory files will be maintained by Surgery Research team and applicable regulatory documents must be completed and on file prior to registration of any patients.

Screening and Informed Consent: Study personnel will identify the patients undergoing pre-operative evaluation at the surgical outpatient clinic (SOPA clinic). All eligible patients (fulfilling the inclusion criteria with no exclusion criteria) will be approached for informed consent.

Randomization: Once consented, eligible patients will be randomized in a 1:1 ratio to treatment with either antibiotic irrigation or placebo irrigation under a blocked randomization scheme. Randomization lists will be prepared by the Department of Biostatistics. When a subject is consented, the study coordinator will assign the patient a study subject number and inform the IDS pharmacist of the study number. The pharmacist will then use the randomization list to assign the randomized medication.

5.0 Treatment Plan

Study Medication: Randomized patients will receive the study drug or placebo intraoperatively during the reconstructive phase of the surgery. The study drug will consist of Polymyxin B (500,000 U) in 1 liter of 0.9% normal saline and the placebo will be 0.9% normal saline. In addition, all patients will receive one dose of parenteral antibiotics within 2 hours of the initial incision. This will consist of 2 grams of intravenous ceftriaxone and 1 gram of intravenous flagyl. For those patients who have allergic contradictions to this regimen, intravenous moxifloxacin (400mg) and clindamycin (600 mg) will be given.

Administration of Study Medication:

- The peritoneal irrigation solution will be manually lavaged over all intended peritoneal surface for a minimum of 60 seconds, but not to exceed 5 minutes. During the irrigation, the operating surgeon will "massage" the solution in the peritoneal surface for another minimum of 60 seconds, less than 5 minutes. The irrigation start and stop time will be recorded. Once this is completed, the residual solution will be cleaned up.

At the end of the reconstructive phase of surgery:

- One (1) Liter of either placebo or study medication will be gently irrigated directly at the pancreateojejunostomy anastomosis or at the pancreatogastrostomy anastomosis, if performed, upon its completion and then removed from the surgical field by suctioning.
- One (1) liter of either placebo or study medication will be gently irrigated at the site of the choledochojejunostomy or hepaticojejunostomy anastomosis at its completion and then removed from the surgical field by suctioning.

Administration of Parenteral Antibiotics:

Within 2 hours (before or after) of initial incision:

- One dose of parenteral antibiotics will be given

Dosing Schedule:

One (1) liter of study drug or placebo will be administered twice via peritoneal irrigation intra-operatively, once at the completion of the pancreateojejunal anastomosis or at the pancreatogastrostomy anastomosis and once at the completion of choledochojejunal or hepaticojejunal anastomosis.

Blinding:

The patient, treating surgeon, and research nurse coordinator will be blinded to the assigned treatment during the course of the study. Upon randomization, the investigational pharmacy will prepare two one liter bags of normal saline solution, either with the antibiotic or just normal saline. During the procedure, the solution will be provided and documentation of the treatment administered will be made as part of the investigational pharmacy documentation.

6.0 Study Calendar

	Baseline	Surgery	Follow up	
	(-30 days-Day 0)	Day 0	Day 30 (+/- 14 days)	Day 90 (+/-14 days) [Telephone Visit]
REQUIRED ASSESSMENTS				
Medical history	x			
Height, Wt	x		x	
Physical examination	x		x	
Vital Signs	x		x	
AE and concomitant medication assessment	x	x	x	
Survival				x
TREATMENT				
Randomization	x*			
Polymyxin B/Placebo Irrigation		x		

x* randomization occurs after patient is registered to the study, prior to surgery

Toxicities to be monitored in this study:

Any evidence of allergic reaction to the antibiotic irrigation will be considered an adverse event.

7.0 Reporting of Adverse Events or Unanticipated Problems involving Risk to Participants or Others

Definitions of Adverse Events

Adverse Event (AE)

An **adverse event** is defined as untoward medical occurrence associated with the use of a drug or procedure in humans, whether or not considered drug or procedure related. An adverse event can be **ANY** unfavorable and unintended sign, symptom, or disease temporarily associated with the use of a medicinal (investigational) product or procedure, whether or not considered related to the medicinal (investigational) product or procedure (attribution of ‘unrelated’, ‘unlikely’, ‘possible’, ‘probable’, or ‘definite’). Examples of Adverse Events that will be recorded in this study are:

- Concomitant illness
- Physical injury
- Events possibly related to medication
- Significant worsening (change in nature, severity, or frequency) of the disease under study or other pre-existing conditions

- Drug interactions
- A laboratory or diagnostic test abnormality occurring shortly after the start of the study that results in the withdrawal of the patient from the study, requires medical treatment or further diagnostic work-up, or is considered by the study investigator to be clinically significant

Adverse events will be graded according to the NCI Common Toxicity Criteria, Version 4.0. Delayed gastric emptying will be graded using the International Study Group of Pancreatic Surgery (ISGPS) system.

Serious Adverse Event (SAE)

A serious adverse event is any untoward medical occurrence resulting in one or more of the following:

- Results in death or ANY death occurring within 28 days of last dose of study drug (even if it is not felt to be drug related)
- Is life-threatening (defined as an event in which the patient was at risk of death at the time of the event; it does not refer to an event which hypothetically might have caused death if it were more severe)
- Requires inpatient hospitalization or prolongation of existing hospitalization

NOTE: Hospitalizations that are not considered SAEs are:

- Hospitalization planned prior to first administration of study drug
- Hospitalization for elective treatment of a pre-existing condition unrelated to the study medication

- Results in persistent or significant disability/incapacity
- Is a congenital anomaly or birth defect
- Is an important medical event (defined as a medical event(s) that may not be immediately life-threatening or result in death or hospitalization but, based upon appropriate medical and scientific judgment, may jeopardize the patient or may require intervention (e.g., medical, surgical) to prevent one of the other serious outcomes listed in the definition above). Examples of such events include, but are not limited to, intensive treatment in an emergency room or at home for allergic bronchospasm; blood dyscrasias or convulsions not resulting in hospitalization; or the development of drug dependency or drug abuse.

Unexpected Adverse Event

An adverse event not mentioned in the package insert or the specificity or severity of which is not consistent with the package insert.

Determining Attribution to the Investigational Agent(s)

Attribution: An assessment of the relationship between the AE and the medical intervention. CTCAE does not define an AE as necessarily *“caused by a therapeutic intervention”*. After naming and grading the event, the clinical investigator must assign an attribution to the AE using the following attribution categories:

Relationship	Attribution	Description
Unrelated to investigational agent/intervention	Unrelated	The AE is clearly NOT related
	Unlikely	The AE is doubtfully related
Related to investigational agent/intervention	Possible	The AE may be related
	Probable	The AE is likely related
	Definite	The AE is clearly related

Adverse Event (AE) Reporting

Adverse events (AEs) will be reported to the principal investigator immediately and will be recorded from the time of first study drug administration until 30 days after surgery, regardless of whether or not the event(s) are considered related to trial procedures or medications. All AEs considered related to trial medication will be followed until resolution, return to baseline, or deemed clinically insignificant, even if this occurs post-trial.

Reporting to the IRB:

1. Unanticipated problems involving risks to subjects or others will be reported **promptly** to the IRB if they:
 - caused harm;
 - were unexpected;
 - were related or possibly related to the research intervention; AND
 - required revision to the informed consent document.

If the serious adverse event does not meet all four (4) criteria listed above, the event does not have to be promptly reported to the Indiana University IRB. However, it will be reported at the time of continuing review.

2. **Prompt** reporting of unanticipated problems to the IRB is defined as within 5 days from becoming aware of the event.

Reporting to the Data Safety Monitoring Committee (DSMC):

Regardless of study sponsorship, the DSMC chair and/or coordinator will review all expedited SAE reports through OnCore®. Expedited reports are completed per IRB guidelines and may include the IRB Prompt Reporting form, non-compliance form. When follow-up information is received, a follow up report will also be created in OnCore. The DSMC chair and/or coordinator will review expedited SAE reports monthly, and report findings to the DSMC.

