9.0 Statistical Considerations

The patients' characteristics will be summarized by treatment arms and compared using two-sample t-tests for continuous and Chi-square test for categorical variables as appropriate. Nonparametric tests will be used if there is a normal distribution assumption violation. All analysis will be performed using SAS 9.3 (Cary, NC)

Efficacy in reducing superficial and organ space infections. In the primary analysis, proportion of patients with infection will be tabled and calculated for each arms and compared using a Chi-square test. In the secondary analysis, we will also use a logistic regression model with infection as the outcome variable, treatment arm as the main predictor, and will adjust for disease process in order to further evaluate the efficacy.

Efficacy in reducing pancreatic fistula rates will be analyzed in a similar way to the primary outcome variable.

Toxicity data related to the treatment will be summarized by treatment arm.

Early Stopping Rule:

An interim analysis will occur after 82 patients have been treated. Overall complication rate and rate of major complication (e.g. Grade 3 through 5) will be analyzed for each treatment group at the interim analysis. If the placebo group infection rate is three (3) times the infection rate of the treatment group, the study will be stopped.

Sample Size and Statistical power: Historical data in hepatopancreatobiliary surgery show that the treated group will reduce primary outcome rate from 24% to 8%. The anticipated reduction in infectious complications was estimated based on historical outcome data for abdominal operations involving one or more gastrointestinal anastomoses. Using a two-sided Chi-square test, we will need 82 patients in each arm to detect such a difference with 80% power and 5% Type I error rate. With no attrition rate, we will need to recruit 164 patients totally. The power analysis was performed for the primary endpoint only.

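### Renal function is not systematically measured or compared between arms, and the final by-arm toxicity summary is limited to events judged related to treatment

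*Combined protocol and SAP*

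**What the plan says.** **Entry.** Section 3.0 excludes allergy to the study medication and, separately, "Serum creatinine > 2.0". The creatinine limit has no unit and no stated reason.

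**Monitoring.** The Section 6.0 calendar has "AE and concomitant medication assessment" at baseline, on the day of surgery and at Day 30. It has no laboratory row at any visit. The only item under the toxicities to be monitored is: "Any evidence of allergic reaction to the antibiotic irrigation will be considered an adverse event".

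**Adverse event rules.** Section 7.0 gives this as one example of an adverse event: "A laboratory or diagnostic test abnormality occurring shortly after the start of the study that results in the withdrawal of the patient from the study". The same item also covers an abnormality that needs treatment or further work-up, or that the investigator considers clinically significant. Events are recorded from first study drug to 30 days after surgery, "regardless of whether or not the event(s) are considered related to trial procedures or medications". On grading: "Adverse events will be graded according to the NCI Common Toxicity Criteria, Version 4.0".

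**Analysis.** Section 9.0 has two by-arm safety statements. The general one is: "Toxicity data related to the treatment will be summarized by treatment arm". The other belongs to the single interim look, set at 82 treated patients, and reads: "Overall complication rate and rate of major complication (e.g. Grade 3 through 5) will be analyzed for each treatment group at the interim analysis". Neither names a renal outcome.

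**The concern.** The allergy exclusion has a matching safety item; the creatinine exclusion has none. Two filters then lie between a change in renal function and the randomized comparison.

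1. **Detection.** No post-operative creatinine is required as data. A change is seen only if someone tests, and recorded only if it leads to action or is judged significant.
2. **Attribution.** The final summary covers toxicity related to the treatment. After an operation with morbidity of around 40% (Section 1.0), a renal event may reasonably be put down to the surgery. If it is, it leaves that summary. For a single patient, a drug effect and an effect of surgery can be hard to tell apart. Comparing the randomized arms is how a trial separates them, and selecting events by attribution first weakens that comparison.

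The hypothesis in Section 2.0 concerns routine use of the irrigation. A positive result could support giving it to every such patient with no systematic renal comparison, from a trial that could have provided one cheaply.

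**Working it through.** **Step 1. Reproduce the plan's sample size.** This fixes the number of patients available for any safety comparison. Inputs from Section 9.0: 24% versus 8%, two-sided 5%, 80% power. With pooled variance and no continuity correction:

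n = [1.960 × √(2 × 0.16 × 0.84) + 0.8416 × √(0.24 × 0.76 + 0.08 × 0.92)]² / (0.24 − 0.08)²

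= (1.0162 + 0.4258)² / 0.0256 = 81.2, so 82 per arm.

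Power at 82 per arm is 80.4%. The stated figure reproduces, and nothing in this point disputes it.

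**Step 2. Follow a post-operative creatinine rise through the plan.**

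| Rise | Recorded? (Section 7.0) | Interim rates (Section 9.0) | Final by-arm summary (Section 9.0) |
|---|---|---|---|
| Not tested | No | No | No |
| Tested, but not treated, worked up or judged significant, and no withdrawal | Not required | No, if not recorded | No, if not recorded |
| Significant, judged unrelated or unlikely | Yes, graded | Could count, inside a total | Not covered |
| Significant, judged possible, probable or definite | Yes, graded | Could count, inside a total | Covered |

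The last column takes the word related in Section 9.0 in the sense of the Section 7.0 attribution table, where possible, probable and definite count as related. The interim analysis states no attribution filter. It covers overall and Grade 3 to 5 complications, not renal events as such, and is specified only at 82 treated, about 82 / 2 = 41 per arm.

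**Step 3. What complete renal data could show.** The documents give no renal event rate, so the control rates below are assumptions. For two proportions:

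power = Φ{[√82 × |p₁ − p₂| − 1.960 × √(2p̄(1 − p̄))] / √(p₁(1 − p₁) + p₂(1 − p₂))}

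| Assumed control rate | Power to detect a doubling | Antibiotic-arm rate detectable with 80% power |
|---|---|---|
| 2% | 11% | 13.7% |
| 5% | 23% | 19.2% |
| 10% | 43% | 26.9% |
| 15% | 64% | 33.7% |

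Worked case, 10% versus 20%: (9.055 × 0.10 − 1.960 × 0.5050) / 0.5000 = −0.168, and Φ(−0.168) = 0.43.

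In terms of precision, with a true rate of 10% in both arms the 95% interval for the difference has half-width 1.960 × √(2 × 0.10 × 0.90 / 82) = 0.092, about 9 percentage points.

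**Step 4. What incomplete detection costs.** Suppose that half of the events are found and recorded in each arm (an assumption). Then 10% versus 27% becomes 5% versus 13.5%, and power falls from 81% to 47%. Likewise, no events among 82 fully measured patients would give a one-sided 95% upper limit of 1 − 0.05^(1/82) = 3.6%. That limit cannot be claimed if an unknown share of patients was never tested.

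**The case against.** The strongest reply is that renal events do have a route into by-arm data. Adverse events are recorded whatever their relationship, significant laboratory abnormalities count, grading is standard, and the interim complication rates carry no stated attribution filter. This stands. A reader might infer from the missing calendar row that renal safety is never compared between arms; the documents do not support that.

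A reader might also infer that the creatinine limit shows that the protocol itself regards the irrigation as a renal risk. The documents do not support that either. The allergy exclusion names the study medication; the creatinine exclusion does not, and it could equally reflect surgical risk. No section describes a renal risk of the drug. Section 5.0 describes irrigation at two anastomoses, each followed by suction, and no absorption figure is given.

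Nor does absence from the calendar prove absence of measurement. The daily drain output and amylase required in Section 8.0 are missing from the calendar too, and a creatinine must be known to apply the exclusion. The baseline value should therefore exist. The gap is that no post-operative value is specified as data anywhere.

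It would be speculation to say that every rise will be blamed on surgery. Possible counts as related, and the surgeon and research nurse coordinator are blinded. The exclusion of events judged unrelated remains, however, whatever their number.

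Finally, the highest inpatient creatinine would be a poor measure. It depends on how often patients are tested and how long they stay. If the irrigation reduces infection, treated patients may be tested less and show lower peaks, which could hide harm. This objection is right and shapes the fix.

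**Conclusion.** The point holds in limited form. Renal function is not systematically measured or compared between arms, and the final by-arm toxicity summary is filtered by investigator attribution. Clinically significant renal events that are found would still be recorded and could enter the interim complication rates.

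No figure in the plan is shown to be wrong, the primary infection comparison is unaffected, and no renal harm is claimed or quantified. The gap concerns all patients given the antibiotic, about 82.

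The conclusion rests on two readings: that the creatinine limit reflects, at least in part, a renal-safety interest, and that the word related in Section 9.0 means attributed by the investigator. If the first is wrong, the case for collecting creatinine weakens, but the case for an attribution-free summary does not. If the second is wrong, one clarifying sentence in Section 9.0 settles that part.

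The change is worth making because it is cheap, not because the trial could settle renal safety: at this size only large differences would be detectable.

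**What to change.** **Section 9.0.** Summarize all recorded adverse events by arm and CTCAE grade for all treated patients, regardless of attribution. The summary of related events can stay as a second table.

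**Section 6.0.** Add renal function to what is monitored, as data capture only. Record the creatinine used for eligibility, with its unit, and the routine post-operative values within one fixed post-operative window that is the same for both arms. The clinical team should set the window before any by-arm data are seen.

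**Reporting.** By arm, give the change from baseline and the CTCAE creatinine grade, each with a 95% confidence interval for the difference between arms. Also give the number of patients with a value and the number of tests, so that a reader can see whether testing differed. Label the comparison descriptive.

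**Cost.** A few chart-abstracted values per patient for 164 patients, and two tables. No change to care is needed if creatinine is measured in routine inpatient practice, which the documents do not state. Two downsides remain. Test frequency may differ by arm even within a fixed window; the counts will show this but not correct it. And with 82 per arm the result is an estimate with a wide interval, not a demonstration of renal safety.
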